## The Effect of an Oral Beta-2 Agonist on Respiratory Muscle Strength in SCI

### Background and Significance:

With an estimated 12,000 incident cases per year, spinal cord injury (SCI) now affects over 300,000 Americans, approximately 52% of whom have injury at the cervical level (tetraplegia) [1]. Although the past 40 years has witnessed a substantial improvement in the acute and chronic management of persons with SCI, mortality remains high during the first year post-injury, and pulmonary complications including pneumonia, lung collapse (atelectasis), respiratory failure, and thromboembolism are the predominant cause [2,3]. History has also seen a shift in the principal cause of mortality during the chronic phase of SCI (> 1 year post-injury); mortality related to urosepsis and renal failure has now been supplanted by pulmonary complications, particularly pneumonia [2]. Thus, pulmonary complications are now the primary cause for premature mortality in the SCI population regardless of time post-injury [2,3].

The propensity for pulmonary complications among subjects with SCI stems from paralysis of respiratory muscles. Injury to the cervical and upper thoracic cord significantly compromises function of the diaphragm, intercostal muscles, accessory respiratory muscles, and abdominal muscles. Respiratory muscle dysfunction is manifest as diminution in lung volumes, reduction in maximal static inspiratory and expiratory mouth pressures (MIP and MEP, respectively), and reduction in peak cough pressure and flow [4]. In a cross sectional analysis of two large outpatient populations with SCI, the forced vital capacity (FVC), or the volume of air forcibly exhaled during a maximal expiratory maneuver, varied inversely with level of lesion; injury levels T6 and above were associated with FVC values below the predicted limits of normal, falling to approximately 50% of predicted at the highest injury levels [5]. Reduced volume and ineffective cough predispose to airway closure and atelectasis, secretion retention, and pneumonia. Residual function of the diaphragm, the principal muscle of inspiration innervated by phrenic nerve roots C3 to C5, is required for unassisted breathing. Excluding C1 and C2 motor complete injuries, most subjects with tetraplegia achieve spontaneous ventilation due to a functioning diaphragm despite intercostal and abdominal muscle paralysis. However, muscle paralysis impairs integrated thoracic expansion during inspiration via alterations in the mechanical properties of the lungs and chest wall, specifically paradoxical downward displacement of the upper rib cage during inspiration [6] and reduced lung and chest wall compliance [7]. These changes in turn are associated with reduction in lung volumes [8,9] and in maximal static mouth pressures (MIP and MEP) [6,7]. Reduced inspiratory capacity directly affects expulsive cough pressure generation and may limit the ability to sigh deeply, both of which may predispose to retained secretions, atelectasis, and increased pneumonia risk [4,10].

Expiratory muscle function is more severely compromised than inspiratory muscle function with higher level SCI given more widespread paralysis of expiratory muscles, principally the expiratory intercostals and abdominal musculature. Residual expiratory muscle function required for forceful expiration (as during exercise) and for effective cough has been attributed to the clavicular portion of the *m. pectoralis major* innervated by nerve fibers originating in the fifth through seventh cervical segments [11] and to the *m. latissimus dorsi* [12]. In patients with neuromuscular disease, conditions often associated with chronic disease progression, diaphragmatic function as reflected by MIP is usually well maintained until late in the disease course, which explains why reduction in MEP compared to MIP has been found to be a more sensitive indicator of progressive respiratory impairment [13]. However, in traumatic cervical SCI, characterized by simultaneous disruption of inspiratory and expiratory muscle function at time of injury, assessment of MIP may confer greater predictive value. Kang et al. found among subjects with tetraplegia that MIP correlated better than MEP with pulmonary function parameters requiring active expiratory effort such as FVC and peak cough flow [14]. Thus, significant decreases in MIP as compared to MEP might better identify individuals with tetraplegia and high paraplegia who are at highest risk for pulmonary complications; impaired inspiratory muscle strength results in further impairment of already significantly compromised expiratory muscle function and cough effectiveness. Indeed, deeper inspiration (greater inspiratory capacity) accompanied by higher MIP is associated with expansion of more distal airways (preventing atelectasis), improvement in expiratory muscle function (better length-tension relationships), and increases in lung elastic recoil pressure [15-17]. Further, in our experience, subjects with high level SCI generally have comparatively lower percent predicted MEP as compared to MIP, again suggesting that deterioration in MIP has greater discriminatory power than subtler decreases in an already depressed MEP for identifying individuals at greatest risk for future pulmonary complications.

Respiratory muscle atrophy and subsequent impaired function are not only the result of muscle paralysis, but also stem from inactivity and deconditioning of residual and neurologically intact respiratory

muscles. Numerous interventional studies in persons with tetraplegia have investigated whether inspiratory and expiratory resistive or threshold training, involving relatively inexpensive portable devices, are effective for improving respiratory muscle strength. Most studies have been uncontrolled and not comparable due to diverse protocols, heterogeneity of subject characteristics, or differences in training techniques [18, 19]. Since 2006, there have been three systematic reviews of respiratory muscle training (RMT) in persons with SCI, and similar conclusions have been drawn; although there is a suggestion that RMT can result in increases in vital capacity and static mouth pressures, the effect size is small, and the data inconclusive[18-20]. Further, there is no evidence of carryover beyond the training period [21]. Insufficient data exists to make conclusions regarding the effects of RMT upon endurance, quality of life, exercise performance, or pulmonary complications [18, 19]. In two of the better designed trials, repetitive training of the clavicular portion of the pectoralis major via isometric exercise for 6 weeks among subjects with tetraplegia resulted in improvements in expiratory muscle strength [22], and a novel approach using non-resistive normocapnic hyperpnea training resulted in significant improvement in respiratory muscle strength and endurance [23]. A systematic review and meta-analysis found a lack of sufficient evidence to either support or discourage use of an abdominal binder to improve respiratory function in SCI [24]. Lastly, interventions to improve inspiratory muscle function via diaphragmatic or phrenic nerve stimulation, or to improve expiratory muscle function and cough strength via magnetic or electrical stimulation can prove highly efficacious, but are often invasive and reserved for highly selected individuals [25].

Pharmacologic interventions to improve respiratory muscle strength have received little attention in the SCI population. A randomized trial with crossover demonstrated that oral theophylline for 6 weeks did not improve pulmonary function in persons with SCI [26]. Studies involving oral beta-2 adrenergic agonists, however, which have been shown to elicit anabolic effects on skeletal muscle in young men [27] and an increase in muscle strength among patients with facioscapulohumeral muscular dystrophy [28], have also demonstrated salutary effects in persons with SCI. One small study showed that administration of an oral beta-2 agonist to subjects with tetraplegia amplified total work output during functional electronic stimulation of leg muscles [29]. In a separate study, it was demonstrated that administration of an oral beta-2 agonist in persons with tetraplegia improved forearm muscle size and strength [30]. On the basis of these reports, we performed preliminary experiments and now have compelling data that lends support to the efficacy of beta-2 agonists for improving respiratory muscle strength in persons with SCI. Salmeterol (Serevent ©) is a long-acting inhaled beta-2 adrenergic agonist approved as a bronchodilator for maintenance management of obstructive lung disease; this agent also exhibits systemic absorption following inhalation [31]. We performed a randomized, double-blind, placebo-controlled, crossover trial of inhaled salmeterol in eleven persons with chronic stable tetraplegia, and found significant improvements compared to matching placebo in lung volumes [FVC, FEV1, expiratory reserve volume (ERV)] and static mouth pressures (MIP and MEP) after 4 weeks of twice daily administration suggesting improvement in lung function and respiratory muscle strength (see Table in Preliminary Studies section) [32]. The medication was well tolerated, and no adverse events were reported. As a follow-up, we recently completed a randomized, double-blind, placebo-controlled, parallel group trial in 30 persons with tetraplegia and high paraplegia (15 subjects each in the active drug and placebo groups) who were administered an oral beta-2 agonist (albuterol repeatabs 4 mg twice daily) versus matching placebo over 12 weeks (data not published). Significant improvements were noted in MIP among subjects who received active drug compared to placebo, and improvements in MEP trended toward significance. Also, it was noted that the greatest increases in MIP were in subjects with the lowest MIP at baseline, suggesting that the weakest individuals targeted by a baseline MIP of < 90 cmH2O would stand to derive the greatest benefit in terms of improvement in respiratory muscle strength and potentially reduction in pulmonary complications.

There are many foreseeable advantages of a pharmacologic approach to improve respiratory muscle strength in persons with SCI. For instance, RMT can be physically demanding and time consuming, compliance can be an issue, and sustainable improvements have not been realized [21, 23]. Perhaps more importantly, in our experience the weakest individuals with SCI who are at greatest risk for recurrent pulmonary complications are the least likely to engage in effort-related protocols. Indeed, our research subjects are often more independent and generally healthier and more willing to engage in research than their weaker counterparts. If we witness what we have documented thus far, we anticipate that most of these issues will be of limited concern given the ease of implementation of this oral medication, the minimal side effects encountered, the minimal time commitment or need for ancillary assistance, and the potential for sustainable effects on respiratory muscle function. Further, it is foreseeable that combination modalities (i.e. pharmacologic and respiratory muscle training regimens) would be possible in motivated individuals. The

ultimate challenge, which remains to be investigated, is whether improvement in respiratory muscle strength and cough effectiveness translates to a decrease in respiratory complications.

Our intent in the present proposal is to enroll a targeted cohort of 24 comparatively weaker subjects with tetraplegia and high paraplegia in a randomized, double-blind, placebo-controlled, parallel group trial to assess the effects of an oral beta-2 agonist upon respiratory muscle strength and cough effectiveness. Based upon the findings from our recent study (please see "Preliminary Studies"), we have chosen a MIP of < 90 cmH2O as a criterion for study inclusion. Use of MIP as the preferred surrogate of underlying respiratory muscle strength in persons with SCI has been previously reported [14]. Individuals will be randomized equally (12 in each group) to receive oral albuterol versus matching placebo for 16 weeks (initial 4 weeks at previous dose of 4 mg twice daily, then in the absence of significant side effects, increased to 8 mg twice daily for the final 12 weeks). If we identify as we anticipate significant improvements in indices of respiratory muscle strength in the active study group after 16 weeks, we intend to repeat testing two weeks later to see if improvements are sustainable. Positive results would dictate the need to pursue a multicenter trial to see if pulmonary complications are reduced, thus making a significant impact on the welfare of this at risk population.

[figure not shown]
#### B. Preliminary Studies

Independent of effects upon respiratory muscle strength, we found that administration of the inhaled beta-2 adrenergic agonist, metaproterenol sulfate, to subjects with chronic stable tetraplegia resulted in a significant increase (>12% and 200 ml) in the forced expiratory volume in one second (FEV1) in 14 of 34 (41%) subjects [33]. We hypothesized that the previously unrecognized airflow obstruction unmasked by bronchodilator administration among subjects with tetraplegia was due to autonomic imbalance; sympathetic (bronchodilating) innervation to the lungs is interrupted, whereas parasympathetic (bronchoconstrictive) neurotransmission carried by vagal nerve fibers remains intact. Support came from a subsequent investigation that employed body plethysmography to measure specific airway conductance (sGAW), a more sensitive indicator of airway caliber and bronchodilation than the FEV1, among subjects with tetraplegia and low paraplegia (injury below T5) [34]. In subjects with tetraplegia but not paraplegia, we found baseline sGAW to be reduced consistent with resting airway narrowing, and witnessed significant increases in sGAW consistent with bronchodilation following inhalation of metaproterenol sulfate. These findings are important to the present proposal insofar as bronchodilation induced by beta-2 agonists can help prevent atelectasis and enhance lung volumes independent of anabolic effects, thereby potentially conferring added benefits.

We performed a preliminary study to evaluate the potential role of a long-acting beta-2 agonist in tetraplegia [32]. Eleven subjects with tetraplegia completed a randomized, double blind, placebo-controlled crossover study. All received placebo or the long-acting beta-2 agonist salmeterol (50ug twice a day from a Diskus inhaler) for 4 weeks with a 4-week washout period. Salmeterol is known to be rapidly absorbed into the systemic circulation following inhalation [31]. Results obtained during the 4th week of salmeterol or placebo administration, regardless of the order of administration, are shown in the following table:

Table 1	Baseline	Placebo	Salmeterol
Total lung capacity (TLC) (L)	5.20±0.47	5.11±0.48	5.32±0.32
Force vital capacity (FVC) (L)	3.11±0.38	3.22±0.41	3.36±0.52*§
Forced expiratory volume in 1 sec (FEV 1 ) (L)	2.40±0.51	2.52±0.49	2.74±0.52*§
Expiratory reserve volume (ERV) (L)	0.51±0.20	0.55±0.17	0.60±0.20●
Residual volume (RV) (L)	2.11±0.45	.89±0.41	1.98±0.44
Maximum inspiratory pressure (MIP) (cmH 2 O)	72.50±18.6	73.9±21.5	81.6±20.8*§
Maximum expiratory pressure (MEP)(cmH 2 O)	40.9±16.6	45.9±19.2	51.3±20.0*§

[figure not shown]
*data are mean±SD; \*p<0.01 versus baseline; §p<0.05 versus placebo; ●p<0.05 versus baseline; L=liters*

[figure not shown]
**Figure 1:** Percent change from baseline in MIP and MEP during phase 1 and phase 2. \* $p < 0.05$  for percent change from baseline.

washout period and into the placebo period (Figure 1), suggesting that sustained increase in MIP and MEP was due to improvement in respiratory muscle strength. Also, a significant increase in the ERV suggested that salmeterol improved expiratory muscle strength (Table 1) [33].

To pursue this question further, we recently completed a randomized, double-blind, placebo-controlled, parallel group trial in 30 persons with tetraplegia and high paraplegia (injury T6 and above). Fifteen subjects each in the active drug and placebo arms were randomized to receive an oral beta-2 agonist (albuterol repeat tabs 4 mg twice daily) versus matching placebo across 12 weeks (data not published). For post-intervention testing, we waited the equivalent of 5 half-lives of the drug to eliminate acute bronchodilator effects; any improvements in pulmonary function were therefore deemed secondary to increases in respiratory muscle strength. We found a statistically significant increase in MIP among subjects who received active drug versus placebo (%change =  $22.7 \pm 19.6$  vs.  $7.5 \pm 17.0$ ;  $p=0.03$ ). The corresponding change in MEP (active drug versus placebo) trended toward significance (%change=  $18.5 \pm 29.1$  vs.  $-0.2 \pm 19.8$ ;  $p=0.06$ ) [Figures 2a and 2b]. In the subset of individuals who received active drug ( $n=15$ ), a statistically significant inverse correlation was found between baseline MIP and change in MIP ( $r^2= -0.326$ ;  $p=0.03$ ), with a trend toward an inverse correlation between baseline MEP and change in MEP [ $(r^2= 0.181$ ;  $p=0.11$ ) [Figures 2c & 2d]. These findings suggest that those with the lowest baseline mouth pressures tended to have the greatest improvement in respiratory muscle strength after receiving oral albuterol (see shaded boxes, Figures 2c & 2d). Thus, administration of an oral beta-2 agonist appeared to elicit the greatest effect on respiratory muscle strength in the weakest individuals, thereby targeting those persons who conceivably stand to derive the greatest benefit. Upon further inspection, a cutoff baseline MIP value of 90 cmH2O identified subjects below which appeared to have the greatest responses to administration of active drug, while those with more “normal” MIP values above this threshold exhibited little improvement. Similar findings were noted with regard to MEP, but did not reach statistical significance. Albuterol was also very well tolerated with minimal side effects; one subject in the active drug group withdrew because of jitteriness.

Patients receiving salmeterol had significant improvement in FVC, FEV1, MIP, and MEP compared to placebo and baseline. Expiratory reserve volume improved during administration of salmeterol compared to baseline (Table 1, Figure 1). Because spirometric parameters improved consistent with bronchodilation, it cannot be stated for certain that improvement in MIP and MEP represented an increase in respiratory muscle strength because both parameters are highly dependent upon the lung volume at which they are measured. However, by considering MIP and MEP values in relationship to whether salmeterol was given first or second, it appeared that improvement in MIP and MEP among those given salmeterol first was sustained through the

**Figure 2:** Oral Beta-2 versus Placebo for a) % change in MIP from FRC, b) % change in MEP from TLC, c) % change versus baseline MIP in active; and d) % change versus baseline MEP in active.

### C. Research Design and Methods:

**PROPOSED STUDY:** This prospective interventional study will be performed at the National Center of Excellence for Medical Consequences of Spinal Cord Injury located at James J. Peters Veterans Affairs Medical Center (JJPVAMC), Bronx, NY. Prior to patient recruitment, approval by the local Institutional Review Board and Research and Development Committee will be obtained. Written informed consent will be obtained from all participants prior to the screening. An oral beta-2 agonist, or placebo, will be administered to subjects with tetraplegia and high paraplegia; the study will be prospective, double-blind with placebo. Subjects will be selected who have no history of asthma, allergies, hypertension or cardiovascular disease. Also excluded will be those already using beta-2 adrenergic agonists, corticosteroids, or antidepressants. Twenty-four patients with tetraplegia (C3-C8) and high paraplegia (T1-T6) who have baseline MIP < 90 cmH2O if male or MIP < 65 cmH2O if female, will be studied. Participants with SCI will be selected from the approximately 120 individuals with SCI who undergo annual pulmonary function testing at our facility. These tests are routinely performed in our pulmonary function lab and interpreted by the principal investigator (~ 120 per year). We estimate that 65% of these subjects will have tetraplegia or high paraplegia (~ 78 subjects), and of these ~ 50% will have a MIP < 90 and 65 cmH2O leaving 39 subjects for enrollment; assuming an attrition rate of 30%, this leaves 27 subjects, more than the 24 anticipated, to complete the trial. Based on power analysis (provided below), we need 12 subjects in each group (albuterol vs. placebo) to have a power of 81% at the alpha of 5%. Subjects will be divided into two groups of twelve, randomized equally to receive sustained-release albuterol repeatabs versus matching placebo over a 16 week period. For the first week, the dosage of albuterol shall be 4 mg every 12 hours as in the previous trial, then in the absence of untoward side effects, increased to 8 mg every 12 hours for the remaining 15 weeks. The study drug/placebo will be dispensed by the VA Research Pharmacy on the subject's first visit and provided at no cost; both study investigators and subjects will be blinded as to study drug. Spirometric parameters, lung volume parameters, diaphragmatic thickness, maximal mouth inspiratory and expiratory pressures (MIP and MEP, respectively), simultaneously obtained esophageal pressure measurements (E-MIP, E-MEP), cough esophageal pressures (C-ESO) will be measured as described below at baseline, after 16 weeks and again at 18 weeks. The flow chart below highlights the test schedule:

Table 2: Procedures To Be Performed.	Baseline	Drug or Placebo	Post	Residual
	Week: 0	Week: 1-16	Week: 16	Week: 18
Pulmonary Function Test and Lung Volumes	X		X	X
Respiratory Muscle Strength Testing	X		X	X
Diaphragmatic Ultrasound	X		X	X
Pulmonary Questionnaire	X		X	X
Take Daily Medication		X		

Weekly Home Pulmonary Function Test		X		
Weekly Self-Symptom Survey		X		
Bi-Weekly Phone Interview		X		

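### 24 is used both as the number randomised and as the number completing, and the plan's three power figures cannot all describe a trial of 24

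*Combined protocol and SAP*

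**What the plan says.** Background and Significance plans to "enroll a targeted cohort of 24 comparatively weaker subjects" and adds: "Individuals will be randomized equally (12 in each group"). Section C (Research Design and Methods) agrees. It names "Twenty-four patients with tetraplegia (C3-C8) and high paraplegia (T1-T6") as those to be studied and states: "Subjects will be divided into two groups of twelve, randomized equally". In all of these, 24 is the number entering treatment.

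Section C's recruitment passage uses 24 differently. About 120 annual tests are reduced to those with tetraplegia or high paraplegia and then to those with low MIP, "leaving 39 subjects for enrollment". It continues: "assuming an attrition rate of 30%, this leaves 27 subjects, more than the 24 anticipated, to complete the trial". Here 24 is compared with the number left after attrition.

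The next sentence sets the size: "Based on power analysis (provided below), we need 12 subjects in each group (albuterol vs. placebo) to have a power of 81" percent, at an alpha of 5%. The only power analysis further down is in section D (Data and Statistical Analysis). It expects d above 0.80, states power above 0.95, and says power stays above 0.85 after 12 dropouts. It gives no N and does not mention 81%.

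Human Subjects Involvement and Characteristics expects about 40 at screening and gives one joint count, 24 to 27, for those who both qualify and finish.

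**The concern.** A count cannot be both the number randomised and the number completing unless nobody is lost in between. The plan does not say that nobody will be lost, and it does not say that more than 24 will be randomised. The sample-size justification (12 per group, 81%) is therefore tied to a number whose meaning changes within one section.

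The power statements do not settle the matter. Losing 12 subjects would halve a trial of 24, yet section D reports more power after that loss than section C reports for the full 24. A reader cannot tell how many will be randomised, how many are expected at week 16, or which N, test and effect size lie behind each power figure.

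**Working it through.** **1. Recruitment arithmetic (inputs from section C).** 120 × 0.65 = 78; 78 × 0.50 = 39; 39 × 0.70 = 27.3, stated as 27. This reproduces. The attrition is 39 × 0.30 = 11.7, or about 12 subjects. Section D's 12 dropouts are 12/39 = 31% of 39 but 12/24 = 50% of 24.

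**2. The 81%.** Two-sample t-test, two-sided 5% (sidedness is not stated, so this is an assumption). Power comes from the noncentral t with n1 + n2 − 2 degrees of freedom and noncentrality d × √(n1·n2/(n1 + n2)). The earlier trial in section B gives d = (22.7 − 7.5)/√((19.6² + 17.0²)/2) = 15.2/18.35 = 0.83. At 12 + 12, power is 47% for d = 0.80 and 49% for d = 0.83, so the stated effect does not reproduce 81%. Solving for 81% at 12 + 12 gives d = 1.212. The plan does not state this value; it is used here only to compare the plan's figures on one footing.

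**3. One test and one effect size (d = 1.212).**

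| N analysed | Split | Noncentrality | Power |
|---|---|---|---|
| 39 | 20 + 19 | 3.78 | 95.8% |
| 27 | 14 + 13 | 3.15 | 85.6% |
| 24 | 12 + 12 | 2.97 | 81.0% (calibrated) |
| 17 | 9 + 8 | 2.49 | 64.6% |
| 12 | 6 + 6 | 2.10 | 47.5% |

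If 24 are randomised and 12 drop out, power is about 48%, not above 85%.

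**4. Does another test rescue all three figures?** A treatment-by-time F test with f = 0.4, three visits and an assumed within-subject correlation of 0.55 gives 0.852 at 12 subjects in total. It then gives 0.995 at 24, not 0.81. A trial of 24 can therefore yield section D's figures or section C's 81%, but not both from one test and one effect size.

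**5. Illustration of loss.** Assume 24 randomised and all 30% lost afterwards: 24 × 0.70 = 16.8, about 17 completers, and 81% falls to about 65%. A treatment-by-time F test calibrated to 81% at 24 gives 64–65% at 17. A one-sided 5% t-test (d = 1.06 for 81%) gives 67%.

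**6. The other meaning of 24.** For 24 completers at 30% loss after randomisation, 24/0.70 = 34.3, so 35 must be randomised, or 36 for equal groups.

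**The case against.** The strongest reply is that attrition is provided for. Read section C as 39 enrolled, about 12 lost, 27 remaining and 24 as the minimum needed. One back-calculated effect size then gives 95.8%, 85.6% and 81% at those three counts, in line with the plan's above 0.95, above 0.85 and 81%. This stands as a coherent reading, so a flat statement that the plan makes no allowance for dropout would go too far. It remains an inference: d = 1.21 appears nowhere in the plan, section D gives no N, and the reading contradicts the two randomised groups of twelve.

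A reader might also infer that the power will be 65%. The documents do not support that. They do not say how the 30% divides before and after randomisation. The 39 is filtered only on injury level and MIP, so the 30% may also have to cover the remaining exclusion criteria and refusals. The joint count in Human Subjects Involvement and Characteristics does not separate the stages.

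Nor does the earlier trial establish a rate of lost data. Section B reports that "one subject in the active drug group withdrew because of jitteriness", but gives active-arm results for n = 15. With t = r√(n − 2)/√(1 − r²) and its r² of 0.181, p is 0.114 at n = 15 and 0.129 at n = 14, against the stated 0.11. The subject who withdrew was apparently replaced or still analysed; the documents do not say which.

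**Conclusion.** The point holds as an internal contradiction. 24 is the number randomised in Background and Significance and in section C's design statements, and the number completing in section C's recruitment sentence. If it is the number randomised, 81% has no margin for loss. If it is the number completing, a 30% allowance may exist, but the statement of how many are randomised is wrong. On neither meaning can 81%, above 0.95 and above 0.85 after 12 dropouts all describe a trial of 24 under one test and one effect size.

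The size is conditional. The fall from 81% to about 65% rests on the back-calculated d, on 24 randomised, on the whole 30% falling after randomisation, and on those lost contributing nothing to the analysis (section D gives no rule for missing data). The actual loss of power cannot be derived from the documents. That d of 0.80 to 0.83 gives only about 47–49% power at 24 is a separate matter and is not counted here.

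**What to change.** Choose one meaning for 24 and use it in Background and Significance, sections C and D, and Human Subjects Involvement and Characteristics. Say how much of the 30% falls before randomisation and how much after.

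- **If 24 are randomised:** replace section D's two power statements with one figure at the number expected to complete, giving N, test, sidedness and effect size. With any loss, it will be below 81% at the same effect size. Possible wording: 24 will be randomised (12 per group); with [x]% loss after randomisation, about [n] are expected to complete week 16, giving power of [y]% ([sidedness], alpha 5%, [test], effect size [d]).
- **If 24 are to complete:** correct the two groups of twelve to the number actually randomised, about 35–36 if the 30% all falls after randomisation. That is within the stated pool of 39 but leaves only 3 or 4 for other exclusions and refusals, so feasibility should be checked. Section D's figures still need their N, test, sidedness and effect size, or removal.

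The first option costs wording only, and the stated power becomes less favourable. The second raises the stated number randomised, with the recruitment that this entails.

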account for equal sample sizes in the placebo and active drug group, and will be forwarded to the research pharmacy wherein the appropriate allocation of placebo/active drug will be dispensed and serve as the official study record.

**Weekly Home Pulmonary Function Assessment:** As a part of monitoring respiratory function, all subjects will be asked to perform weekly spirometry measurements using a portable spirometer [Microlife Digital Peak Flow & FEV1 Meter (Microlife Corporation, Dunedin, FL)]. This device will allow subjects to check and record peak flow and other relevant parameters of a forced expiration. Subjects will be given detailed instructions and a demonstration on a first visit to ensure their understanding of the device and the maneuvers they will need to perform. Upon turning on the device, subjects will be prompted to take a maximal breath in and then to exhale forcefully through a mouthpiece. Subjects will be instructed to close their lips around the mouthpiece to prevent air leak that could affect the measurement. The device will automatically record the results, and the dates and times of recording. All participants will be asked to perform three consecutive maneuvers preferably upon awakening in the morning.

**Weekly Self-symptom Survey:** Subjects will be asked to fill out a questionnaire [37] regarding their symptoms on a weekly basis, the responses for which will be entered into a master database on each visit.

**Bi-weekly phone interview:** A member of the investigative team will contact the subject over the phone on a biweekly basis to speak about any symptoms or changes in lung function that the subject may be experiencing or have experienced since a previous discussion. The phone interview will only last a few minutes. The subject will be reminded that they are allowed to contact a member of the study team at any point should they have a question or emergency.

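### The protocol gives two different times for the albuterol dose increase, so the planned dose in weeks 2 to 4 is not defined

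*Combined protocol and SAP*

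**What the plan says.** Two places in the current text set out the regimen of the proposed trial.

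- **Background and Significance, closing study overview.** Participants take albuterol or matching placebo for 16 weeks: "initial 4 weeks at previous dose of 4 mg twice daily", and then, "in the absence of significant side effects, increased to 8 mg twice daily for the final 12 weeks".
- **Section C, Research Design and Methods, paragraph on the proposed study.** The treatment period is again 16 weeks: "For the first week, the dosage of albuterol shall be 4 mg every 12 hours as in the previous trial", and then, "in the absence of untoward side effects, increased to 8 mg every 12 hours for the remaining 15 weeks".

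Three other items bear on the point.

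- Section C also says "The study drug/placebo will be dispensed by the VA Research Pharmacy" and places this at the first visit.
- Table 2 has a single row, "Take Daily Medication", marked once for weeks 1 to 16, with no dose level and no escalation week.
- Table 2 lists a "Bi-Weekly Phone Interview" over the same weeks. The text explains that a team member will "contact the subject over the phone on a biweekly basis", without giving the date of the first call.

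**The concern.** Both passages describe the same trial: 24 participants, 12 per group, albuterol against matching placebo for 16 weeks. They put the dose increase at different times, after week 4 in one and after week 1 in the other. Following one breaches the other. A participant taking 16 mg per day in week 3 is on plan under section C and at twice the planned dose under the overview.

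What is at stake is whether the experimental regimen is defined. Instructions for weeks 2 to 4 have to be written when study drug is dispensed. Adherence and dosing deviations in those weeks need a reference schedule. The increase is conditional on tolerability, so its date also fixes when that judgement is made. Any report of the trial must state one regimen.

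**Working it through.** **Inputs.** All come from the two passages quoted above. Twice daily and every 12 hours are the same frequency, so the 4 mg step is 8 mg per day and the 8 mg step is 16 mg per day.

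**Step 1: reproduce the stated duration.**

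- Overview: 4 + 12 = 16 weeks.
- Section C: 1 + 15 = 16 weeks.

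Both match the stated 16 weeks (16 × 7 = 112 days; 112 × 2 = 224 doses). The total therefore does not expose either version as a slip.

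**Step 2: compare the schedules by week, for a participant who escalates.**

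| Weeks | Overview | Section C | Agree? |
|---|---|---|---|
| 1 | 8 mg/day | 8 mg/day | yes |
| 2–4 | 8 mg/day | 16 mg/day | **no** |
| 5–16 | 16 mg/day | 16 mg/day | yes |

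The dispute is confined to days 8 to 28, which is 21 days: 21/112 = 18.75% of treatment days, or 42/224 = 18.75% of scheduled doses.

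**Step 3: planned exposure.** Total = (days at 4 mg twice daily × 8) + (days at 8 mg twice daily × 16), assuming escalation and every dose taken.

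| | Overview | Section C |
|---|---|---|
| Doses | 56 of 4 mg + 168 of 8 mg = 224 | 14 of 4 mg + 210 of 8 mg = 224 |
| Days 8–28 | 21 × 8 = 168 mg | 21 × 16 = 336 mg |
| Whole course | 28 × 8 + 84 × 16 = 1,568 mg | 7 × 8 + 105 × 16 = 1,736 mg |
| Mean per day | 1,568/112 = 14.0 mg | 1,736/112 = 15.5 mg |
| Weeks at higher dose | 12/16 = 75% | 15/16 = 93.75% |

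Difference: 1,736 − 1,568 = 168 mg, and 168/1,568 = 10.7%. For a participant who does not escalate, the two schedules are identical.

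**Step 4: look for something that settles it.**

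- Table 2 does not, because its medication row is undivided.
- The documents contain no amendment log and no statement of precedence.
- The regimen of 4 mg twice daily for 12 weeks in Preliminary Studies belongs to the completed 30-person trial and does not explain the difference.

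**Two side observations, neither needed for the conclusion.**

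- The condition for the increase is worded as *significant* side effects in one place and *untoward* in the other. The documents do not show that these set different thresholds.
- The meaning of *biweekly* affects how many scheduled calls come before the increase. If calls are every 14 days and the first is on day 14 (an assumption), none precedes day 8 (section C) and two precede day 29 (overview). If calls start in week 1, or are twice a week, at least one call can come first under either schedule.

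**The case against.** The strongest reply is that the two passages do not have equal standing. One is an overview inside a background section. The other is in the methods, is headed as the proposed study, and uses operative language, so a reader would probably follow it; the overview may simply be unrevised text. This is a reasonable guess about how the conflict arose, but the protocol does not say it. The overview presents itself as the intent of the present proposal and gives a complete regimen. A dosing instruction should not depend on inferring the rank of sections.

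A second reply is that little follows for the analysis. Both versions share the drug, the two dose levels, the frequency, the total duration, week 1 and weeks 5 to 16. Formal testing is at baseline, week 16 and week 18, so anyone who escalates on schedule has at least 12 weeks at the higher dose before the week 16 test under either version. This stands. The conflict does not bias the randomised placebo comparison, and it does not show that participants would be dosed differently from one another.

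A third reply is that pharmacy orders and review-board papers, which are not among these documents, may already fix one schedule. That is possible, and it limits the claim: dosing in weeks 2 to 4 cannot be checked against this protocol. If such papers exist, they will agree with one passage and contradict the other.

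Finally, no passage makes a phone call the gate for the increase, and participants may contact the team at any time. The count of calls therefore carries no weight here.

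**Conclusion.** The contradiction is real and must be fixed. Two current passages give incompatible times for the same dose increase, and nothing in the documents resolves them. The dispute covers 21 of 112 days (18.75%), with a twofold difference in planned daily dose in that window. The whole-course difference is 168 mg (10.7% of the overview's total), assuming that the participant escalates and takes every dose; it is zero for a participant who does not escalate.

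The consequence is an undefined regimen in weeks 2 to 4, which affects dispensing, adherence, the timing of the tolerability judgement and the reported treatment. It is not a threat to the validity of the randomised comparison. The severity rests on the principle that a conditional dose increase in an interventional trial must be stated one way only.

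**What to change.** The investigators should reconcile the overview in Background and Significance with section C so that one schedule, and one wording of the condition for the increase, appears throughout. Table 2 should show that schedule, for instance by one added line marking the dose step. The reconciled text should then be checked against the pharmacy and review-board documents. While making the change, the investigators should say what *biweekly* means for the phone interviews and have regard to the participant contacts that Table 2 already lists.

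The cost is protocol wording, one table line and a document check. Sample size, endpoints and analysis are unaffected. Which schedule is right is for the investigators to settle; none is proposed here.
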